### 5.2.2. Exclusion Criteria

A patient will not be eligible for inclusion in this study if any of the following criteria apply:

- 1. Has received prior biological, cytotoxic or hormonal (other than for replacement) therapy to treat this incidence of breast cancer.
- 2. Has received prior radiation therapy to the chest to treat this incidence of breast cancer.
- 3. Is a pregnant or lactating female.
- 4. Has malabsorption syndrome, disease affecting gastrointestinal function, or resection of the stomach or small bowel.
- 5. Is considered medically unfit for the study by the PI as a result of the medical interview, physical exam, or screening investigations.

- 6. Has a history of drug or other allergy, which, in the opinion of the PI makes contraindicates participation.
- 7. Has a known immediate or delayed hypersensitivity reaction or idiosyncrasy to drugs chemically related to the study medication. These include other anilinoquinazolines, such as gefitinib [Iressa], erlotinib [Tarceva], or other chemically related compounds.
- 8. Has received treatment with any investigational drug in the previous 4 weeks.
- 9. Currently receiving treatment with any medications listed on the prohibited medication list (see Section 8.2).
- 10. Has had major surgery within the previous 2 weeks.
- 11. Aspartate or alanine transaminase (ALT or AST) greater than three times the upper limit of normal (ULN).
- 12. Has physiological, familial, sociological, or geographical conditions that do not permit compliance with the protocol.
- 13. Has Class III or IV heart failure as defined by the NYHA functional classification system.
- 14. Has a left ventricular ejection fraction (LVEF) < 50% based on MUGA or ECHO.
- 15. In the clinical judgment of the investigator or designated staff the patient has inadequate venous access for the protocol required blood draws.

### 5.2.3. Other Eligibility Criteria Considerations

To assess any potential impact on subject eligibility with regard to safety, the investigator must refer to the following document(s) for detailed information regarding warnings, precautions, contraindications, adverse events, and other significant data pertaining to the investigational product(s) being used in this study. Such documents include the Clinical Investigator's Brochure (CIB) [GlaxoSmithKline Document Number RM2000/00481/06].

Patient Requirements and Restrictions:

• Patients must notify the PI about any concomitant medications taken from the time of screening through study completion.

### 6. STUDY ASSESSMENTS AND PROCEDURES

The study specific assessments and procedures are detailed below and are outlined in the Time and Events Schedule contained in Section 14.1, Appendix 1. The total amount of blood to be obtained during this study is approximately 60 mL.

# 6.1. Demographic and Baseline Assessments

Demographic data will include date of birth, race, height in centimeters, and body weight in kilograms. For height and weight measurements, the patient will be allowed to wear indoor daytime clothing with no shoes.

Baseline characteristics will include a comprehensive physical examination, medical conditions, and concomitant medications. The medical and physical examination should be performed by a qualified physician and should include a thorough review of all body systems. All data will be captured in the Case Report Form (CRF) and study database.

# 6.2. Screening Visit

Screening assessments will be completed within 14 days prior to the first dose of study drug. Screening assessments completed within 72 hours of first dose can be used as Day 1 assessments. After consent has been obtained, patients will be required to undergo a medical screen to determine whether they are eligible to participate in the study according to the criteria listed in Section 5.2. Additionally, evaluations at the Screening visit will include:

- Full physical examination, including vital signs (blood pressure and heart rate).
- Medical history including date of diagnosis of current incidence of breast cancer, histology and current sites of disease.
- Medication history
- 12-lead ECG.
- MUGA or ECHO.
- Hematology (Section 14.2, Appendix 2).
- Clinical Chemistry including serum pregnancy test for women of childbearing potential (Section 14.2, Appendix 2).

All required information will be captured in the patient source records and documented in the CRF. Any results falling outside of the normal ranges may be repeated at the discretion of the PI.

# 6.3. On Study Assessments

On Day 1 and on the day prior to surgical resection patients will have safety, pharmacokinetic and pharmacodynamic assessments performed. The following procedures will be completed and time and date of each assessment will be documented in the source records and the CRF.

- Full physical examination, including vital signs (blood pressure and heart rate) to occur at Day 1 (if greater than 14 days since screening physical exam) and prior to scheduled surgical resection.
- Clinical Chemistry on Day 1 (if greater than 14 days since screening chemistries) and prior to scheduled surgical resection.
- Hematology on Day 1 (if greater than 14 days since screening hematology) and prior to scheduled surgical resection.

- A blood sample for pharmacokinetic analysis will be collected pre-dose on Day 1 and at the time of surgical resection. Refer to Section 6.6 for sampling schedule.
- Pharmacodynamic sampling (1 x 5 mL tubes of whole blood) on Day 1 and the on the day prior to scheduled resection. Refer to Section 6.7 for sampling schedule.
- Pharmacogenetic sampling (1 x 10 mL tube of whole blood) on Day 1 or at any time during the conduct of the study. Refer to Section 6.8 for sampling schedule.
- Assessment of study medication compliance when study medication bottle is returned prior to surgical resection.
- Assessment of adverse events continuously.
- Tumor surgical resection (≥Day 10).

# 6.4. Post Study Visit

Seven to twenty-eight days following the last dose of lapatinib (or prior to initiating adjuvant therapy), all patients will be required to have a post-study evaluation to include:

- Full physical examination, including vital signs (blood pressure and heart rate).
- Medication history.
- Assessment of Adverse Events.
- Clinical Chemistry.
- Hematology.
- Pharmacodynamic sampling (1 x 5 ml tube of whole blood).

### 6.5. Safety

# 6.5.1. Pregnancy

The investigator, or his/her designee, will collect pregnancy information on any female subject who becomes pregnant while participating in this study. The investigator, or his/her designee, will record pregnancy information on the appropriate form and submit it to GSK within 2 weeks of learning of a subject's pregnancy. The subject will also be followed to determine the outcome of the pregnancy. Information on the status of the mother and child will be forwarded to GSK. Generally, follow-up will be no longer than 6 to 8 weeks following the estimated delivery date. Any premature termination of the pregnancy will be reported.

While pregnancy itself is not considered to be an AE or SAE, any pregnancy complication or elective termination of a pregnancy for medical reasons will be recorded as an AE or a SAE, as described in Section 10.6, "Recording of AEs and SAEs" and will be followed as described in Section 10.8, "Follow-up of AEs and SAEs."

A spontaneous abortion is always considered to be a SAE and will be reported as described in Section 10, "Adverse Events (AE) and Serious Adverse Events (SAE)."

Furthermore, any SAE occurring as a result of a post-study pregnancy **and** is considered reasonably related to the investigational product by the investigator, will be reported to GSK as described in Section 10.11, "Post-study AEs and SAEs." While the investigator is not obligated to actively seek this information in former study participants, he/she may learn of an SAE through spontaneous reporting.

### 6.5.1.1. Pregnancy testing

All women of child-bearing potential will have a serum  $\beta$ -hCG test performed at screening.

As positive serum  $\beta$ -hCG test result at screening will exclude the patient from participation in the study (See Section 5.2).

### 6.5.1.2. Action to be taken if pregnancy occurs

A patient who has a positive  $\beta$ -hCG test result at any time after study drug administration will have study drug terminated immediately. All post-treatment study assessments will be collected as described in Section 6.5.

### 6.5.2. Clinical Laboratory Tests

Blood will be obtained for clinical laboratory tests prior to dosing on Days 1 and the day prior to surgical resection.

### 6.5.3. Cardiac Assessments

A 12-lead ECG and MUGA or ECHO will be obtained at the Screening visit.

### 6.5.3.1. Primary Cardiac Endpoint

The following is a definition of a primary cardiac endpoint, which includes cardiac death and congestive heart failure. This definition is provided to universally describe cardiac-related events.

- Cardiac death defined as either:
  - Cardiac death due to heart failure, myocardial infarction or arrhythmia;
  - Probable cardiac death defined as sudden, unexpected death within 24 hours of a definite or probable cardiac event.
- Severe symptomatic congestive heart failure defined as:
  - New York Heart Association (NYHA) class III or IV (refer to Appendix 5) (class III defined as being not capable of climbing one flight of stairs and class IV defined as having symptoms at rest), and
  - A drop in left ventricular ejection fraction (LVEF) of more than 10 points from baseline **and** below 50%.

Treatment with lapatinib will be permanently stopped if a subject develops severe symptomatic NYHA class III or IV event and has a drop in LVEF of more than 10 points. However, all efforts must be made to complete all post-study patient assessments which must include LVEF measurement. The method for LVEF assessment at screening should be used to assess LVEF in 4 weeks after documented absolute decrease of 10 points from baseline, and every 4 weeks for at least 16 weeks or until resolution.

### 6.5.3.2. Secondary Cardiac Endpoint

- Asymptomatic or mildly symptomatic cardiac event defined as:
  - An asymptomatic (NYHA I) or mildly symptomatic (NYHA II) significant decrease in LVEF defined as an absolute decrease in LVEF of more than 10 points from baseline and
  - LVEF value below 50%.

A second LVEF assessment must be performed within approximately 3 weeks to confirm the significant decrease in LVEF as defined above. If a subject has a confirmed secondary cardiac event as defined above, cardiac evaluation, preferably using the same method as for LVEF baseline assessment, must be performed every 4 weeks for at least 16 weeks or until resolution.

#### 6.5.4. Adverse Events

Patients will be monitored from screening until 28 days after the last dose (or until initiation of adjuvant chemotherapy) for the occurrence of AEs.

### 6.5.5. Criteria for Study Hold

If Grade III or IV toxicity is observed in  $\geq 30\%$  ( $\geq 3$  patients) of the first 10 patients the study will placed on hold (i.e. no further accrual). The safety data will be reviewed jointly by the GSK medical monitor and the Principal Investigators to determine if termination of additional enrollment is warranted.

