# 5.1. Number of Subjects

A sufficient number of patients will be enrolled to obtain approximately 20 evaluable patients approximately 16 study centers. Evaluable subjects are defined as those subjects whose pre-treatment tumors are determined by a central laboratory to be ErbB2 positive, which is defined as either IHC 3+ or FISH amplified. Patients must have pre-dose and post-dose tumor tissue samples adequate for biomarker analyses, and have completed lapatinib treatment for a minimum of 9 days. In addition, the elapsed time between last lapatinib dose and surgical resection must be within 24 hours.

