# 7.4. Treatment Assignment

All patients will receive 1500 mg of lapatinib daily. Any patient not completing all required assessments will be replaced.

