#### Additional protocol defined criteria:

- All grade 4 laboratory abnormalities.
- Cardiovascular events have been seen in patients taking other compounds that inhibit ErbB2 when used in combination with or following anthracyclines and interstitial pneumonitis has been reported in patients taking compounds that inhibit ErbB1. As a precaution, the following will be reported as SAE:
  - Cardiac related events meeting the criteria of a primary cardiac endpoints (which is, CHF and cardiac death) will be reported as serious adverse events (SAEs).

Note: If a secondary cardiac endpoint fulfils any of the criteria for 'seriousness' (e.g. hospitalisation), it must also be reported as an SAE. **Symptomatic** declines in LVEF that do not meet the criteria for a secondary cardiac endpoint are not expected to be common. These events will be reported as AEs or SAEs, if applicable, as described above. **Asymptomatic** declines in LVEF that do not meet the criteria for 'significant,' do not qualify as a secondary cardiac endpoint and will not be reported as AEs.

Any signs or symptoms of pneumonitis that are ≥ Grade 3 (NCI CTCAE, version 3.0) (defined as radiographic changes and requiring oxygen). Refer to [Cancer Therapy Evaluation Program, 2003] CTCAE (version 3.0) grading of pneumonitis/pulmonary infiltrates.

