## 10.7. Evaluating AEs and SAEs

#### 10.7.1. Assessment of Intensity

The investigator will make an assessment of intensity for each AE and SAE reported during the study. The assessment will be based on the investigator's clinical judgment and using the Cancer Evaluation Program, Common Terminology Criteria for Adverse Events(CTCAE), Version 3, when appropriate. For non-CTCAE graded events, the intensity of each AE and SAE recorded in the CRF should be assigned to one of the following categories:

Mild: An event that is easily tolerated by the subject, causing minimal discomfort and not interfering with everyday activities.

Moderate: An event that is sufficiently discomforting to interfere with normal everyday activities.

Severe: An event that prevents normal everyday activities.

An AE that is assessed as severe should not be confused with a SAE. Severity is a category utilized for rating the intensity of an event; and both AEs and SAEs can be assessed as severe. An event is defined as 'serious' when it meets one of the pre-defined outcomes as described in Section 10.2, "Definition of a SAE".

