# 10.9. Prompt Reporting of SAEs to GSK

SAEs will be reported promptly to GSK as described in the following table once the investigator determines that the event meets the protocol definition of an SAE.

| 10.9.1. | Timeframes for | Submitting | SAE Re | ports to GSK |
|---------|----------------|------------|--------|--------------|
|         |                |            |        |              |

|             | Initial SAE Reports |                    | Follow-up Information on a
Previously Reported SAE |                            |
|-------------|---------------------|--------------------|---|----------------------------|
| Type of SAE | Time Frame          | Documents          | Time Frame  | Documents                  |
| All SAEs    | 24 hrs              | "SAE" CRF
pages | 24 hrs  | Updated "SAE"
CRF pages |

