#### 11.4.1. Withdrawal

Patients that drop out will be replaced until 20 subjects have been determined to be evaluable.

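### The 30% toxicity hold counts only the first 10 patients, so Grade III/IV events in patient 11 onward, about half or more of those treated, meet no study-level threshold

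*Supplement*

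**What the plan says.** Section 6.5.5 (Criteria for Study Hold) is the only study-level numeric toxicity limit in the current protocol. Grade III or IV toxicity in at least 30%, given as at least 3 patients, "of the first 10 patients the study will placed on hold (i.e. no further accrual"). The medical monitor and the investigators then review the safety data jointly "to determine if termination of additional enrollment is warranted". A hold is therefore a prompt for review and need not end the study.

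The number treated goes well past 10. Section 5.1: "A sufficient number of patients will be enrolled to obtain approximately 20 evaluable patients approximately 16 study centers". Section 7.4: "Any patient not completing all required assessments will be replaced". Section 11.4.1: "Patients that drop out will be replaced until 20 subjects have been determined to be evaluable". Patients enter on a local ErbB2 result (Section 5.2.1). They are evaluable only with central confirmation, adequate paired tissue, at least 9 days of dosing and surgery within 24 hours of the last dose (Section 5.1). The number treated may thus exceed 20.

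The safeguards that apply to every patient are these:
- Section 10.9: "SAEs will be reported promptly to GSK", with a 24-hour limit. The SAE definition in Section 10.2 adds "All grade 4 laboratory abnormalities", the primary cardiac endpoints and pneumonitis of Grade 3 or more.
- Section 6.5.3.1: permanent stop for one patient after a severe cardiac event.
- Section 9.2: the investigator may discontinue a patient.
- Section 12.2: periodic review of study data by monitors.
- Section 12.4: the sponsor may suspend or stop the study at its discretion.

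**The concern.** The plan treats 30% as the level at which more patients should not enter before someone has looked, but it counts toward that level only the toxicity of the first 10. If 2 of the first 10 and 5 of the next 10 are affected, the total is 7/20 = 35% and no pre-set review follows. In the extreme, 2 + 10 = 12 of 20 (60%) could be affected without meeting the rule.

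Serious-event reporting does not fully close this gap, because the plan separates severity from seriousness: "An AE that is assessed as severe should not be confused with a SAE" (Section 10.7.1). A Grade III event that is not serious and not on the extra list is recorded but prompts no expedited report. With about 16 centers for about 20 evaluable patients, a single investigator may see only one or two patients, so a pooled rate shows only if someone keeps a tally. After the first 10, the protocol ties no action to one.

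The stakes are limited. Everyone receives the same fixed dose, so the value of counting on is more data about one rate, not the detection of an expected late rise.

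**Working it through.** **The plan's own figure.** 3/10 = 30%, so the rule is consistent with itself.

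**Share of patients whose events are not counted**, (N − 10)/N. With no replacements, 10/20 = 50%. The non-evaluable rate is not given. At assumed rates of 10, 20 and 30%, N = 20/(1 − d), rounded up, is 23, 25 and 29, and the share is 13/23 = 57%, 15/25 = 60% and 19/29 = 66%.

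**Rule as written.** P(hold) = 1 − P(X ≤ 2), with X ~ Binomial(10, p). The documents give no true rate p for this trial, so 10 to 40% is an illustrative range.

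**Extended rule.** Hold at the third affected patient among the first 10, then at ceil(0.3n) affected among n treated for n > 10: 4 for n = 11–13, 5 for 14–16, 6 for 17–20, 7 for 21–23, 8 for 24–26. The probability of a first hold at each n comes from an exact recursion on the running count, stopping at the boundary. The inputs are 20 treated, each outcome known before the next patient enters (no lag), and independent patients.

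A first hold at patient 20 of 20 stops nobody, so it is shown separately.

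| True rate | As written | Extended, hold before patient 20 | Extended, including patient 20 |
|---|---|---|---|
| 10% | 7.0% | 7.9% | 7.9% |
| 20% | 32.2% | 38.3% | 39.3% |
| 30% | 61.7% | 72.3% | 74.1% |
| 40% | 83.3% | 92.0% | 93.2% |

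At 30%, the first-hold probabilities after patient 10 are 0.0210 (n = 12), 0.0327 (13), 0.0114 (15), 0.0197 (16), 0.0075 (18), 0.0136 (19) and 0.0182 (20), and zero at 11, 14 and 17. They sum to 0.1241. Removing the last leaves 0.1059, and 0.6172 + 0.1059 = 0.7231, which agrees with the table to rounding.

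**Patients spared.** Suppose each added hold ends accrual and D further patients are already dosed when it is called. The mean per trial is the sum over n > 10 of P(first hold at n) × max(0, N − n − D). At 30%, N = 20 and D = 0 this is 8(0.0210) + 7(0.0327) + 5(0.0114) + 4(0.0197) + 2(0.0075) + 1(0.0136) = 0.56.

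| D | 0 | 2 | 4 | 6 | 8 |
|---|---|---|---|---|---|
| N = 20 | 0.56 | 0.36 | 0.19 | 0.07 | 0 |
| N = 24 (assumed replacements) | 1.08 | 0.81 | 0.56 | 0.36 | 0.19 |

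The documents give no accrual rate, so D is also illustrative.

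**The case against.** The strongest answer is proportionality. The plan chose an early check followed by discretion, and nowhere promises continuous numeric monitoring. Dosing can be as short as 9 days. Section 7.3 reports good tolerability at 1200 and 1600 mg once daily and no maximum tolerated dose up to 1800 mg/day, and Section 1.4 notes that the drug is already approved in combination at 1250 mg. This stands, and it is why the point has low priority. It does not explain why 3 of 10 calls for a review and 7 of 20 does not.

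A reader might infer that the trigger expires when patient 11 enters. The text does not support that. The rule counts toxicity in the first 10 whenever it appears, and Section 6.5.4 follows patients to 28 days after the last dose or to adjuvant chemotherapy. A late third event in that group still stops accrual.

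A reader might also infer that nobody watches safety after patient 10. That is wrong too: the safeguards listed above all continue. What they lack is a study-level number.

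The gain must not be overstated either. Holds at patient 20 of 20 are 0.0182/0.1241 = 15% of the apparent gain at a true 30%. With four more patients already dosed, only first holds by patient 15 spare anyone: 0.0210 + 0.0327 + 0.0114 = 0.065, about half of it. With about 16 centers, such overlap is plausible.

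Finally, a bare cumulative rule would misfire after a restart. A trial resumed with 4 of 10 affected would be held again at patient 11 with no new event. That objection is right, and the fix below meets it.

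**Conclusion.** The point holds in a limited form. The 30% hold applies only to toxicity in the first 10 patients, and events in about half or more of those treated count toward no study-level threshold. Extending it adds 10.6 percentage points to the chance of a hold that can still stop accrual at a true 30%, 6.1 at 20% and 0.8 at 10%, with 20 treated and no lag.

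The benefit in patients is modest. At a true 30% it is at most 0.56 of 20 on average. It falls to zero with 8 already dosed and reaches about one patient only if replacements bring the number treated to 24 and there is no lag. All of these assume that each added hold ends accrual, which Section 6.5.5 does not say. Even extended, the rule would miss 26% of trials at a true 30%. The protocol names no unacceptable true rate, so this is no failed design property. It is a cheap improvement of the lowest priority.

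**What to change.** Keep Section 6.5.5 as it is, including the immediate hold at a third affected patient among the first 10. Add two provisions:

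1. After the 10th patient, the same 30% threshold applies cumulatively to all treated patients until accrual ends, with the same joint review: hold at 4 of 11–13, 5 of 14–16, 6 of 17–20, 7 of 21–23 and 8 of 24–26.
2. If accrual resumes after a reviewed hold, a further hold requires at least one new patient with Grade III or IV toxicity since that review and the cumulative boundary met, unless the review sets a different next trigger.

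The cost is a short paragraph and a running tally of grades that are already collected. First review holds rise by about 1 point at a true rate of 10% and by 6 to 7 points at 20%. These figures count first holds only, so some repeat reviews come on top in trials that resume. If the sponsor prefers the present rule, a sentence saying why the limit is confined to the first 10 would do.
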